5. STUDY DESIGN

Study GZHA is a Phase 1, single-site, randomized, placebo controlled, single-ascending dose (SAD) study in healthy participants, to evaluate the safety, tolerability, and PK of LY3493269 administered as single SC doses and as a single IV dose. The PD effects of SC doses of LY3493269 on glycemic effects (including fasting glucose, insulin, and glucose and insulin during an oral glucose tolerance test [OGTT]) and appetite will be explored. For the SC cohorts, the investigator and participants will be blinded. The IV Cohort is open label with no placebo.

The planned LY3493269 SC doses for this study range from 0.15 mg to 7.5 mg. These dose levels may be adjusted (for example, dose increments may be reduced, a dose level may be repeated, or a lower/intermediate dose may be administered) based on ongoing review of available safety, tolerability, PK, and PD data. Any proposal to adjust SC or IV doses from those planned and stated in the protocol, together with supporting data, will be reviewed by an independent safety review panel.

Participants will undergo safety (including but not limited to adverse events [AEs], medical assessments, clinical laboratory tests, body weight, vital signs and ECGs]), PK and PD assessments.

Subcutaneous Administration Cohorts 1 through 6

This study includes up to 6 planned SC cohorts:

- SC Cohort 1: 0.15 mg (6 LY3493269: 2 Placebo)
- SC Cohort 2: 0.5 mg (6 LY3493269: 2 Placebo)
- SC Cohort 3: 1.5 mg (6 LY3493269: 2 Placebo)
- SC Cohort 4: 3.0 mg (6 LY3493269: 2 Placebo)
- SC Cohort 5: 5.0 mg (6 LY3493269: 2 Placebo)
- SC Cohort 6: 7.5 mg (6 LY3493269: 2 Placebo)

Cohorts 2 to 6 will be initiated only if the investigator and Eli Lilly and Company clinical pharmacologist deem the safety results in the preceding cohort to be acceptable through Day 8 from at least 6 participants dosed. In addition, all planned participants in the current cohort should have been dosed prior to escalation to the next cohort.

Intravenous Administration Cohort

This study includes a single IV cohort (IV Cohort), where up to 6 healthy participants should complete dosing at the same level to provide sufficient PK sampling. The IV Cohort will be initiated based on review of safety and tolerability data from SC Cohort 3 and available 7-day PK data and/or PD data from at least 2 preceding SC cohorts.

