8. DEFINITION OF ANALYSIS POPULATIONS

The "Safety" population will consist of all subjects who received at least one dose of study drug or placebo.

The "Pharmacokinetic" population will consist of all subjects who received at least one dose of study drug and have evaluable PK data.

The "Pharmacodynamic" population will consist of all subjects who received at least one dose of study drug or placebo and have evaluable PD data.

All protocol deviations that occur during the study will be considered for their severity/impact and will be taken into consideration when subjects are assigned to analysis populations.

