9.3.2 Pharmacokinetic Statistical Methodology

PK dose proportionality will be assessed. Log-transformed C_{max} , AUC(0-t_{last}) and AUC(0- ∞) of LY3493269 will be evaluated using a power model (where log-dose acts as an explanatory variable) to estimate ratios of dose-normalized geometric means and corresponding 90% confidence intervals (CIs). The estimated ratio of dose-normalized geometric means of PK parameters between the highest and lowest doses will be used to assess dose proportionality. A subinterval within the highest and lowest doses may also be considered for assessment of dose proportionality using the same approach.

A statistical analysis using the Kruskal-Wallis test³ will be conducted to investigate the dose proportionality (independence) of t_{max} . The p-value will be calculated for the overall dose comparison.

All PK parameters will be summarized using descriptive statistics. Geometric means of the IV dose group and corresponding SC dose group will be used to discuss absolute bioavailability.

Examples of the SAS code that will be used are as follows:

```
proc mixed data=xxx;
model log_pk = log_dose / alpha=0.1 cl solution outpred=resids ddfm=kr;
estimate 'xx mg' intercept 1 log_dose yy / alpha=0.1 cl; /*Log value of xx*/
estimate 'zz mg - xx mg' log_dose pp / alpha=0.1 cl; /*Difference in log
values of zz and xx*/
ods output solutionf=est;
ods output estimates=estims;
run;
```

Kruskal-Wallis Test

```
proc npar1way data=xxx
  class dose;
  var pk;
  output out=krusk;
run;
```

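### SAP 9.3.2: the example contrast gives the un-normalised high-to-low ratio, not the stated dose-normalised one, and the SC-only scope of the power model and tmax test is not written down

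*SAP*

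**What the plan says.** SAP 9.3.2, in line with Protocol 10.3.2.2, fits a power model to log-transformed Cmax and AUC "to estimate ratios of dose-normalized geometric means and corresponding 90% confidence intervals". The estimated ratio "between the highest and lowest doses will be used to assess dose proportionality".

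The example code that follows has three relevant lines:

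- the model: "model log_pk = log_dose / alpha=0.1 cl solution outpred=resids ddfm=kr"
- a fitted value at one dose: "estimate 'xx mg' intercept 1 log_dose yy / alpha=0.1 cl"
- the contrast between two doses: "estimate 'zz mg - xx mg' log_dose pp / alpha=0.1 cl". A code comment defines `pp` as the difference between the two log doses.

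For tmax, the same section runs a Kruskal-Wallis test with `dose` as the class variable.

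SAP 8 defines the PK population as "all subjects who received at least one dose of study drug and have evaluable PK data", with no restriction by route. SAP 6 lists 0.5 mg SC and 0.5 mg IV as separate treatments. In 9.3.2 the IV group is mentioned only for the descriptive discussion of absolute bioavailability.

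**The concern.** There are two gaps between the text and the code.

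1. **Estimand.** The text calls for a dose-normalised ratio, for which 1 means proportional. The response in the code is not divided by dose and the contrast does not subtract the log dose ratio. What comes out, once exponentiated, is the raw ratio of geometric means. Its reference value is the dose ratio, not 1. Neither the code nor the text states the step from one to the other.

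2. **Analysis set.** The PK population includes the IV cohort, and neither procedure has a route term or filter. A class variable of dose cannot tell 0.5 mg IV from 0.5 mg SC. If the IV dose were raised to its permitted 1.5 mg, it would coincide with SC Cohort 3 instead. An IV bolus has a different Cmax and a much earlier tmax than an SC dose, so pooling would let a route difference look like a dose effect.

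At stake is the dose-proportionality statement under the secondary PK objective.

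**Working it through.** The plan gives no numerical result on this point to reproduce, so the check is algebra followed by a sensitivity analysis.

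**Part 1: the contrast**

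Inputs: lowest SC dose 0.15 mg and highest 7.5 mg (SAP 5), so ln(7.5/0.15) = ln 50 = 3.912.

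Model: ln(PK) = a + b·ln(dose).

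- Coded contrast: b × 3.912, which back-transforms to 50^b.
- Stated estimand: [GM(7.5)/7.5] ÷ [GM(0.15)/0.15] = 50^(b − 1).

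| Slope b | Coded contrast, exponentiated | Dose-normalised ratio |
|---|---|---|
| 0.9 | 33.8 | 0.676 |
| 1.0 | 50.0 | 1.00 |
| 1.1 | 73.9 | 1.479 |

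The predictions in Protocol Table GZHA.2 show the same gap:

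- AUC: 386000/7670 = 50.3 raw, and 50.3/50 = 1.007 normalised.
- Cmax: 1580/31.2 = 50.6 raw, and 50.6/50 = 1.013 normalised.

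One simulated data set was fitted (six SC doses, six participants each, exact proportionality, assumed log-scale SD 0.3). The coded contrast gave 46.9 (90% CI 37.1 to 59.2). With log(PK/dose) as response, the same contrast gave 0.937 (0.742 to 1.18). Dividing the first set by 50 gives the second exactly.

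**Part 2: what pooling IV would do to the power model**

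Take exact SC proportionality, six values at each of the six SC doses, and six IV values at 0.5 mg whose level is r times the SC level.

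- With seven equal groups, the mean log dose is 0.264 and the sum of squared deviations is 12.10 per participant.
- The 0.5 mg point lies 0.957 below the mean.
- The fitted slope is therefore b = 1 − (0.957/12.10) × ln r = 1 − 0.0791 × ln r.

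The documents do not give r for Cmax, so it is an assumption. A one-compartment model with F = 1 gives IV C0 = AUC × ln 2/half-life. Using the Table GZHA.2 starting-dose predictions (AUC 7670, SC Cmax 31.2) and assumed half-lives:

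| Assumed half-life | IV C0 | r | Slope | Normalised Cmax ratio, 50^(b − 1) |
|---|---|---|---|---|
| 168 h | 31.6 | about 1.0 | 1.00 | 1.00 |
| 120 h | 44.3 | 1.4 | 0.973 | 0.90 |
| 72 h | 73.8 | 2.4 | 0.931 | 0.76 |

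For AUC, r is 1/F. Protocol 7.5 expects SC bioavailability close to 100%, so r is near 1 and the ratio stays near 1.00. If F were 80% (assumption), r = 1.25 and the ratio would be 0.93.

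**Part 3: what pooling IV would do to the tmax test**

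Protocol Section 2 has the first postdose SC sample at 6 h. IV sampling starts at the end of administration, then 15 and 30 min. Kruskal-Wallis at 5% was simulated 4000 times with the same assumed tmax distribution at every SC dose and IV tmax set near zero. SC tmax took the values 6, 12, 24, 48 and 72 h.

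| Assumed probabilities | SC only | IV pooled at 0.5 mg |
|---|---|---|
| 0.05, 0.15, 0.50, 0.25, 0.05 | 3.3% | 38.4% |
| 0, 0.10, 0.40, 0.40, 0.10 | 3.5% | 37.2% |

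Other assumed SC tmax distributions gave 35% to 38% pooled and about 4% SC only. A fair summary is about 36% against 4%.

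**The case against.** The code is introduced as examples and is full of placeholders, including the data set name. The governing text names the right estimand. The code does not exponentiate either, so some post-processing is plainly intended. The slope and its 90% CI are written to an output data set, from which the dose-normalised ratio follows directly. A value near 50 would also be noticed by anyone expecting a number near 1.

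On the IV cohort, a missing filter in template code is weak evidence. Read just as literally, the same step would mix Cmax with AUC, because it has no selection by parameter. The SAP keeps the routes apart elsewhere: separate treatment labels in SAP 6, and separate IV and extravascular parameters in SAP 9.3.1. The TFL shells, which are not available here, may settle the matter.

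The consequences are limited too. The study is not powered for hypothesis tests, no acceptance bounds are set for the ratio, and escalation rests primarily on safety (Protocol 7.4.1).

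Most of this stands, and it rules out two stronger readings. A reader might infer that the trial will report an invalid proportionality result. The documents do not support that, because the estimate and both limits rescale exactly by a known constant. A reader might also infer that IV pooling is planned. The documents show only that it is not excluded. What remains is that the SAP, which supersedes the protocol's statistical section, leaves both the normalising step and the analysis set to the programmer.

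**Conclusion.** The point holds as a minor specification gap. The example contrast estimates the un-normalised ratio. For the planned range it is too large by a factor of 50 relative to the stated estimand, and the factor changes if the dose range changes. The correction is exact and loses nothing.

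The SC-only scope of the power model and the tmax test is unstated. The sizes in Parts 2 and 3 are conditional on pooling happening at all, and they rest on assumed half-lives, a one-compartment model with F = 1, and assumed tmax distributions. At a half-life of about 168 h the Cmax effect vanishes. Even when pooled, the tmax test fails to reject in roughly 64% of runs, so pooling raises the false-positive rate without making a dose effect on tmax certain to appear. AUC is hardly exposed if bioavailability is as expected.

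**What to change.** Make two edits to SAP 9.3.2.

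1. Use log(PK/dose) as the response, in which case the existing contrast gives the stated estimand. Alternatively, keep log PK and state that the reported ratio is exp((slope − 1) × ln(high/low)), with the slope's 90% limits transformed the same way.
2. State that the power model and the Kruskal-Wallis test of tmax use SC cohorts only, and add that restriction to both example procedures. The IV group stays in the descriptive bioavailability comparison.

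The cost is about two lines of text or code. Trial conduct, data collection and sample size are unaffected.

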9.4 Pharmacodynamic Assessment

9.4.1 Pharmacodynamic Analysis

The oral glucose tolerance test (OGTT) will be used to derive the following PD endpoints/biomarkers by Covance:

- Fasting (Pre-OGTT) glucose, insulin, C peptide and glucagon. Baseline for these parameters will be the Day -1 Pre-OGTT concentration.
- Concentrations of glucose, insulin, C peptide and glucagon during the OGTT. Baseline for these parameters will be the time-matched Day -1 Pre-OGTT concentration.
- AUC(0-2h) for glucose, insulin, C peptide and glucagon during the OGTT, derived using the trapezoidal rule. Baseline for these parameters will be the Day -1 AUC.

In addition, the following OGTT derived parameters will also be derived:

• HOMA-IR and HOMA-B based on fasting insulin and fasting glucose^{4,5}

 $HOMA - IR = (FPI \times FPG)/22.5$

$$HOMA - B = (20 x FPI)/(FPG - 3.5)$$

where FPI = fasting plasma insulin in μ U/mL, FPG = fasting plasma glucose in mmol/L

Or alternatively,

$$HOMA - IR = (FPI \times FPG)/405$$
$$HOMA - B = (360 x FPI)/(FPG - 63)$$

where FPI = fasting plasma insulin in μ U/mL, FPG = fasting plasma glucose in mg/dL

• Insulinogenic index^{4,5}

$$IGI = \frac{\Delta Insulin_{0-30min}}{\Delta Glucose_{0-30min}}$$

where glucose is in mg/dL and insulin is in μ U/mL

• Insulin sensitivity (Matsuda Index)⁶

$$ISI = \frac{10000}{\sqrt{G0 * I0 * \frac{Glucose AUC(0-2h)}{2h} * \frac{Insulin AUC(0-2h)}{2h}}}$$

where glucose is in mg/dL and insulin is in $\mu U/mL$

• $OGIS^7$

$$OGIS = \frac{1}{2} \times (B + sqrt(B^2 + 4 \times p5 \times p6 \times (G90 - Gcl) \times Cl_{OGTT}))$$

where, $B = (p5 \times (G90 - Gcl) + 1) \times Cl_{OGTT}$
 $Cl_{OGTT} = p4 \times \frac{\frac{p1 \times D_0 - V \times \frac{G120 - G90}{T}}{G90} + \frac{p3}{G0}}{I90 - I0 + p2}$

$$p1 = 6.50, p2 = 1951, p3 = 4514, p4 = 792, p5 = 11.8 \times 10^{-3}, p6 = 173$$

D₀, glucose dose of OGTT normalized for body surface area (mmol/m²)

- $V = 10^4$ (glucose distribution volume, ml/m²)
- T = 30 (time interval between G120 and G90, min)
- Gcl = 5 (typical clamp glucose concentration, mmol/L)
- OGIS (ml/min.m²)

BMI (kg/m²)

Fasting glucose (mmol/L)

Fasting insulin (pmol/L)

2h Glucose (mmol/L)

Predicted clamp-derived insulin sensitivity (M value)⁸

 $log_{e}PREDIM = A + B \times log_{e}(OGIS) + C \times log_{e}(BMI) + D$ $\times log_{e}(2hGlucose) + E \times log_{e}(FastingInsulin)$

 $PREDIM = e^{log_e(PREDIM)}$

where A = 2.8846219, B = 0.5208520, C = -0.8223363, D = -0.4191242, E = -0.2427896 and OGIS = OGTT derived Oral glucose insulin sensitivity index

Individual observed (spaghetti plots) and mean time profile of the postdose PD parameters, including baseline corrected parameters, will be plotted by treatment group.

Absolute values as well as change from baseline fasting glucose, insulin and C-peptide will be analyzed statistically. Parameters will be untransformed before statistical analyses. The parameters will be analyzed using mixed-effects repeated measures (MMRM) models to evaluate treatment effects as well as treatment comparisons. The model will include treatment, timepoint, and treatment-by-timepoint interaction as fixed effects, and subject as a random effect. Baseline values will be included as a covariate for the change from baseline analysis. An unstructured covariance structure will be used and a compound symmetry structure may be used if this fails to converge. Least-squares means as well as 90% CIs for the difference of LY3493269 compared with placebo will be reported.

Example of SAS code (for the change from baseline analysis) as follows.

```
proc mixed data=xxx;
class treatment timepoint subject;
model change = baseline treatment timepoint treatment*timepoint
/residual ddfm=kr;
repeated timepoint / subject=subject type=UN;
lsmeans treatment*timepoint / cl pdiff alpha=0.1;
ods output lsmeans=lsm diffs=estims;
run;
```

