# 2. Schedule of Activities

Study Schedule Protocol J1X-MC-GZHA – for Subcutaneous Cohorts

Procedure	Screening				ment Period:	SC (	Coho	rt				Fo	llow-	up	Comments/ Notes
Days	-28 to -2	-2	-1	1	2	3	4	5	6	8	15	29	43	ET	
2 1 1 2											± 1	± 3	± 3		
Study informed consent	X														
Medical history	X														
Physical examination/ Medical assessment	X		X	P	X			X	X	X	X	X	X	X	Complete physical examination at screening. Symptom-directed physical examination across study at other timepoints.
Height and weight	X			P						X	X	X	X	X	Height at Screening only.
Confirmation of eligibility followed by randomization		X													
Admit to CRU		X													
Discharge from CRU – on completion of inpatient procedures							X								Participants may remain inpatient longer than Day 4, at the investigator's discretion.
Administer study drug				X											Refer to Section 7.1.
AEs/ concomitant medications	X		X	X	X	X	X	X	X	X	X	X	X	X	
Vital signs: supine BP and PR (h)	X			P, 1, 4, 6, 12	24	48	72	96	120	168	X	X	X	X	For Day 15 and subsequent visits, vital signs should be measured within 30 min of the scheduled PK sample.
Body temperature (h)	X			P, 6, 12	24										
ECG – single	X											X	X	X	

Procedure	Screening			Treat	ment Period:	SC (	Coho	rt				Fo	llow-	-up	Comments/ Notes
Days	-28 to -2	-2	-1	1	2	3	4	5	6	8	15	29	43	ET	
ECG – triplicate (m, h)				-30m, -15m, 0, 1, 4, 6, 12h	24	48	72	96	120	168	X X	±3	±3		Day 1 Predose ECGs will be taken in triplicates at - 30, -15 and 0 min to establish a baseline. Day 15 ECG should be measured within approximately 30 min of the PK sample.
Clinical safety lab tests (fasted)	Х			P	Х		X			X	X	X	X	X	
Serology  • Hepatitis B surface antigen, Hepatitis B core antibody  • Hepatitis C antibody  • HIV	Х														
Point of care safety glucose samples				Pre-n lun	Days 1 – 3: neals (breakfa ch and dinner before bedtim	)	X	X	X						Days 4 -6: Fasted samples collected before breakfast.
PK sampling (h)				P, 6, 12	24	48	72	96	120	168	X	X	X	X	Days 15, 29, 43 and ET: Samples collected anytime during visit. The ET sample is not required for participants who discontinued without receiving IP.
OGTT – 75 g glucose challenge (h)			X		24										Conducted following overnight fast.

Procedure	Screening			Treat	ment Period:	SC (	Coho	rt				Fo	llow-	up	Comments/ Notes
Days	-28 to -2	-2	-l	1	2	3	4	5	6	8	15	29	43	ET	
											±1	±3	±3		
PD biomarkers (h):			Pre-OGTT,	P	Pre-OGTT,	48	72			X	X	X			Days 1, 3, 4, 8, 15 and 29:

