#### Protocol J1X-MC-GZHA

Subcutaneous Dosing Cohorts

Purpose	Blood Volume per Sample (mL)	Approximate Number of Blood Samples	Approximate Total Volume (mL)
Screening tests a (local laboratory)	23	1	23
Clinical laboratory testsa (local laboratory)			
Study visits	10	5	50
Follow-up/Early discontinuation visit	8	3	24
LY3493269 pharmacokinetics	5	12	60
Potential additional LY3493269	5	3	15
pharmacokinetic samples			
Blood discard for cannula patency	0.3	13	3.9
Point-of-care safety glucose (on-site)	0.3	15	4.5
Pharmacodynamics (central laboratory)			
Glucose	2	16	32
Insulin, C-peptide	3	16	48
- CCI			
Pharmacognostic cample (stored)	10	I I	10
Pharmacogenetic sample (stored)	10	1	10
Non-pharmacogenetic sample (stored)			
• Plasma	2	4	8
• Serum	2.5	4	10
• P800	2	4	8
Immunogenicity	10	4	40
Total			390.9
Total for clinical purposes (rounded up to the	nearest 10mL)		400

a Additional samples may be drawn if needed for safety purposes.

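### The fasting glucose, insulin and C-peptide baseline is valid but leaves a second predose fasting sample unused; averaging the two would narrow intervals at almost no cost

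*SAP*

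**What the plan says.** SAP 9.4.1 takes the fasting values from the OGTT visits and fixes their baseline: "Baseline for these parameters will be the Day -1 Pre-OGTT concentration". (The sentence also covers glucagon, which is not among the analytes modelled and lies outside this point.)

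The modelling text is: "Absolute values as well as change from baseline fasting glucose, insulin and C-peptide will be analyzed statistically". On the terms: "The model will include treatment, timepoint, and treatment-by-timepoint interaction as fixed effects, and subject as a random effect". On adjustment: "Baseline values will be included as a covariate for the change from baseline analysis". On output: "Least-squares means as well as 90% CIs for the difference of LY3493269 compared with placebo will be reported". Neither the text nor the example SAS code lists the levels of timepoint.

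In the protocol's Schedule of Activities for the SC cohorts, the PD biomarker row reads, across Days -1 to 4, "Pre-OGTT, P Pre-OGTT, 48 72"; the P is a predose draw on Day 1. The note beside that row requires a fast of at least 8 hours for "Days 1, 3, 4, 8, 15 and 29". Appendix 5 budgets the samples as "Insulin, C-peptide 3 16 48" (mL per sample, number of samples, total mL), and glucose also has 16.

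Protocol 5.1.1 places the SC cohorts' baseline assessments, including PD blood sampling, on Day -1.

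**The concern.** Each SC participant gives two fasting values before dosing, about a day apart, and the SAP uses one of them. A single fasting value carries day-to-day noise. In a covariate-adjusted change analysis, that noise weakens the adjustment and so widens the interval for each dose against placebo. With six active participants per dose, a gain from data already collected is worth having.

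A second, smaller matter is that the Day 1 predose value has no stated role and the model's timepoints are not listed. The SAP therefore does not say in so many words that this value stays out of the response vector.

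**Working it through.** **1. Is the Day 1 predose sample really planned?** Count the SC schedule: Day -1 OGTT 5 (pre-test plus 0.5, 1, 1.5 and 2 h), Day 1 predose 1, Day 2 OGTT 5, and Days 3, 4, 8, 15 and 29 one each.

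5 + 1 + 5 + 5 = 16, which matches Appendix 5. Without the Day 1 draw the count is 15. The sample is planned and budgeted.

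**2. Inputs for precision**
- Six active participants per dose (protocol 5.1).
- One Placebo SC treatment group (SAP section 6), so 6 × 2 = 12 pooled placebo participants and 6 × 8 = 48 SC participants.
- Residual degrees of freedom at one timepoint: 48 − 7 groups − 1 covariate = 40.
- Standard deviation and correlation of fasting values: not given. Results are in SD units and the correlation is an assumption.

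**3. Formulas.** Let rho be a common correlation among all fasting values, with unit variance.
- Residual variance given one baseline: V1 = 1 − rho².
- Residual variance given the mean of two: V2 = 1 − 2rho²/(1 + rho).
- Ratio: V2/V1 = (1 + 2rho)/(1 + rho)².
- 90% half-width: t(0.95, 40 df) × √(1/6 + 1/12) × √V = 1.684 × 0.5 × √V.

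Example at rho = 0.5: V1 = 0.75 and V2 = 1 − 0.5/1.5 = 0.667. The ratio is 0.889 and √0.889 = 0.943, so the interval is 5.7% narrower.

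| rho (assumed) | V1 | V2 | Half-width, Day -1 only | Half-width, mean of two | Narrower by |
|---|---|---|---|---|---|
| 0.3 | 0.910 | 0.862 | 0.803 | 0.781 | 2.7% |
| 0.5 | 0.750 | 0.667 | 0.729 | 0.687 | 5.7% |
| 0.7 | 0.510 | 0.424 | 0.601 | 0.548 | 8.9% |
| 0.9 | 0.190 | 0.147 | 0.367 | 0.323 | 11.9% |

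**4. A less favourable pattern.** Let the two baselines correlate at rb with each other and at a lower rp with post-dose values. Then V2 = 1 − 2rp²/(1 + rb) and V1 = 1 − rp².
- rb 0.9, rp 0.5: V2/V1 = 0.737/0.750 = 0.982, 0.9% narrower.
- rb 0.9, rp 0.7: ratio 0.949, 2.6% narrower.
- rb 0.8, rp 0.5: ratio 0.963, 1.9% narrower.
- rb 0.8, rp 0.7: V2/V1 = 0.456/0.510 = 0.893, 5.5% narrower.

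**5. Where the gain applies.** It applies to the change-from-baseline model, which carries the baseline covariate. No covariate is stated for the absolute-value model, so redefining baseline does not touch it.

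**6. If the Day 1 predose value did enter as a response.** Timepoints would rise from 6 to 7, and unstructured covariance parameters from 6 × 7/2 = 21 to 7 × 8/2 = 28. In a simulation of 1,500 trials under two correlation patterns, with the covariance treated as known, the standard errors of the post-dose contrasts moved by at most 0.024 SD. Simulation error is roughly 0.40/√(2 × 1,500) = 0.007 per entry. This does not test the cost of estimating seven more parameters, but it shows no material effect on the contrasts themselves.

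**The case against.** The strongest reply is that nothing here is wrong. Day -1 is where protocol 5.1.1 puts baseline PD sampling. It is the like-for-like match to the Day 2 pre-OGTT value, and it supplies the fasting inputs to HOMA, Matsuda and OGIS. Any predose baseline gives an unbiased randomised comparison. All of this stands.

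A reader might infer an inconsistency because clinical laboratory tests, vital signs, body weight and appetite VAS take Day 1 predose as baseline. The documents do not support that. In the SC schedule those measures have no Day -1 assessment (protocol 5.1.1 mentions a Day -1 VAS, but the schedule does not), so the different baseline follows from what is collected.

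A reader might also infer that the plan will analyse a predose value as a treatment response. It does not say so. SAP 9.4.1 calls the plotted profiles postdose, the table shells are a separate document, and an analyst would most likely model post-dose visits only. A compound symmetry fallback is already provided if the unstructured fit fails.

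On size, the gain depends on an undocumented correlation, the endpoints are exploratory, and the study is not powered for hypothesis testing. These points limit the importance of the change. They do not remove the case for using a sample already drawn. SAP 9.5.6 itself averages repeated predose ECGs to form a baseline, though those are taken on the same day.

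**Conclusion.** The point holds as an inexpensive improvement. The single Day -1 baseline is valid, but it leaves a second fasting predose value unused in the change-from-baseline analyses of fasting glucose, insulin and C-peptide. Averaging the two narrows the 90% interval for an active-placebo difference by about 3% to 12% for rho from 0.3 to 0.9 under equal correlations, and by about 1% to 6% under the less favourable patterns tried. Both ranges rest on assumed correlations, because the documents give none. They also assume pooled placebo and complete data.

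The documents do not show that the Day -1 choice is an error, that it biases any comparison, or that baseline adjustment is the main source of precision. The unlisted timepoints are a matter for clarification only.

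**What to change.** In SAP 9.4.1:
- For the change-from-baseline analyses of fasting glucose, insulin and C-peptide, define baseline as the mean of the Day -1 pre-OGTT and Day 1 predose fasting values, or the available one if the other is missing.
- Keep Day -1 as baseline for the OGTT time courses, the AUCs and the OGTT-derived indices.
- List the response timepoints of the fasting MMRM as Days 2, 3, 4, 8, 15 and 29.

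The cost is SAP wording and the matching derivation, with no new samples or visits. There are two small downsides. The Day 1 fast follows the Day -1 75 g glucose load by about 24 hours, equally in all SC arms. The fasting endpoints would also have a different baseline from the OGTT indices, which a table footnote should state. If the sponsor prefers Day -1 alone, the timepoint list and a sentence on how the Day 1 predose value is handled are still worth adding.

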#### 10.3.3.2. Pharmacodynamic Statistical Inference

Pharmacodynamic parameters may be transformed before statistical analyses, if deemed necessary. Absolute values as well as change from baseline in each parameter will be analyzed using mixed-effects models to evaluate treatment effects as well as treatment comparisons. The model will include treatment, day, and treatment-by-day interaction as fixed effects, and participant as a random effect. Baseline values, as well as other influencing variables, may be used as covariates.

All PD parameters, including baseline-corrected parameters, will be summarized and tabulated by treatment group and day. Summary statistics will be provided. The individual observed and mean time profile of the postdose PD parameters will be plotted by treatment group.

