9.5.9 Appetite Analysis

To explore the effects of LY3493269 on meal intake and appetite sensation, subjects will be asked to rate their appetite sensations using a 100-mm visual analog scale (VAS) for parameters of hunger, fullness, satiety, and prospective food consumption prior to dosing on Day 1, and in the fasted state while inpatient as well as on scheduled outpatient visits.

The VAS is presented as a 10-cm (100-mm) line, anchored by verbal descriptors, usually "extremely" and "not at all". Subjects are required to rate their subjective sensations on four 100 mm scales combined with questions similar to the following:

- 1. "How hungry do you feel?"
- 2. "How satisfied do you feel?"
- 3. "How full do you feel?"
- 4. "How much do you think you could eat?"

A staff member will use a caliper to measure the distance from 0 to the mark that the subject placed on the VAS and record the measurement in the source document. Overall appetite score is calculated as the average of the 4 individual scores: [satiety + fullness + (100-prospective food consumption) + (100-hunger)] / 4.

The individual VAS measurements and overall appetite score will be listed and summarized by treatment and timepoint, alongside change from baseline (Day 1 predose).

The individual parameters, and overall score, will be analyzed using an MMRM model to evaluate treatment effects as well as treatment comparisons. The model will include treatment, timepoint, and treatment-by-timepoint interaction as fixed effects, and subject as a random effect. An unstructured covariance structure will be used and a compound symmetry structure may be used if this fails to converge. Least-squares means as well as 90% CIs for the difference of LY3493269 compared with placebo will be reported. The distribution of the data will be tested prior to analyses and should the distribution indicate a parametric analysis not to be

appropriate, a non-parametric analysis will be used instead. Change from baseline (Day 1 predose) will also be analysed, with a covariate for baseline added to the model.

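### The absolute-value models for fasting glucose, insulin, C-peptide and the appetite scores leave out the baseline covariate, so the SAP reports a second, unadjusted set of drug-placebo differences beside the adjusted change-from-baseline set

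*SAP*

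**What the plan says.** SAP 9.4.1 analyses three fasting markers on two scales: "Absolute values as well as change from baseline fasting glucose, insulin and C-peptide will be analyzed statistically". The general model statement has no baseline term: "The model will include treatment, timepoint, and treatment-by-timepoint interaction as fixed effects, and subject as a random effect". Baseline then enters one of the two analyses: "Baseline values will be included as a covariate for the change from baseline analysis". The example code in that section is labelled as being for the change analysis. The reported output is stated once, for both scales: "Least-squares means as well as 90% CIs for the difference of LY3493269 compared with placebo will be reported".

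SAP 9.5.9 follows the same pattern for appetite: "The individual parameters, and overall score, will be analyzed using an MMRM model to evaluate treatment effects as well as treatment comparisons". After describing that model without baseline, it adds: "Change from baseline (Day 1 predose) will also be analysed, with a covariate for baseline added to the model".

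Eight endpoints are therefore modelled twice: three fasting markers, four VAS items and the overall appetite score. Neither SAP section says which scale takes precedence. Vital signs (SAP 9.5.5) and body weight (SAP 9.5.10) are modelled only as change from baseline with the covariate, so they are not affected.

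Protocol 10.3.3.2 asks for both scales and leaves the covariate optional: "Baseline values, as well as other influencing variables, may be used as covariates". Protocol Section 4 (Table GZHA.1) defines the fasting-marker and appetite endpoints as changes from baseline.

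**The concern.** The two models estimate the same drug-placebo difference at each dose and timepoint, but one conditions on baseline and the other does not. With six participants per dose, groups will differ at baseline by chance, and the absolute-value contrast carries part of that difference. The report could then show two unequal estimates of one effect, sometimes with opposite signs, and the gap would say nothing about the drug.

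Protocol 5.4 says preliminary PD data will help identify the dose range for later studies. Two conflicting tables with no stated precedence leave room to choose between them after the results are seen.

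**Working it through.** The documents give no power, precision or correlation figure for these models, so there is no plan figure to reproduce.

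**Inputs**
- 6 active and 2 placebo per SC cohort, up to six cohorts (SAP Section 5).
- One pooled placebo group of 6 × 2 = 12. This is inferred from the single SC placebo row in SAP Section 6 and needs all six cohorts to run.
- 6 × 8 = 48 SC participants in 7 groups (six doses and placebo).
- Baseline-postdose correlation ρ: not given. Assumed at 0.3, 0.5 and 0.7, with equal SDs at baseline and postdose.

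**1. Size of chance imbalance.** SD of the baseline difference, in baseline SDs = √(1/6 + 1/12) = √0.25 = 0.50.

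**2. How much reaches the absolute-value contrast.** Given a baseline difference d, the expected shift is slope × d, where slope = ρ × SD(post)/SD(pre), which is ρ when the SDs are equal. For d = 0.50 SD:
- ρ = 0.3: 0.3 × 0.50 = 0.15 SD
- ρ = 0.5: 0.5 × 0.50 = 0.25 SD
- ρ = 0.7: 0.7 × 0.50 = 0.35 SD

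Simulation (20,000 trials per ρ, one postdose timepoint) gave slopes of 0.31, 0.50 and 0.69 for the unadjusted contrast and about 0 for the adjusted one.

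**3. Precision.** The unadjusted SE is 0.50 SD, so the 90% CI half-width is 1.683 × 0.50 = 0.84 SD (41 degrees of freedom). With the covariate, SE = 0.50 × √[(1 − ρ²)(1 + 1/39)], where 39 = 48 − 7 − 2 and the last factor is the cost of estimating the slope.

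| ρ | Adjusted SE (SD) | Adjusted / unadjusted | Unadjusted SE larger by |
|---|---|---|---|
| 0 | 0.506 | 1.013 | none; adjusting costs 1.3% |
| 0.3 | 0.483 | 0.966 | 3.5% |
| 0.5 | 0.439 | 0.877 | 14% |
| 0.7 | 0.362 | 0.723 | 38% |

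The two SEs are equal when (1 − ρ²)(1 + 1/39) = 1, that is ρ² = 1/40 and ρ ≈ 0.16.

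**4. Disagreement in sign.** With no drug effect, the adjusted and unadjusted estimates of a single contrast had opposite signs in about 10%, 17% and 25% of simulated trials at ρ = 0.3, 0.5 and 0.7.

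**5. Does the covariance structure supply the adjustment?** The plan is "An unstructured covariance structure will be used and a compound symmetry structure may be used if this fails to converge". In a generalised least squares check with a full covariance matrix, six postdose timepoints, ρ = 0.7 and complete data, the absolute-value contrast at the last timepoint was −0.257. That was exactly the raw postdose mean difference, whether or not predose was entered as a response level. The baseline imbalance in that dataset was −0.583. The covariance structure does not remove it.

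**6. Effect of adding baseline.** Change is value minus baseline. With baseline in both models, only the baseline coefficient differs (by 1), and the treatment contrasts are the same. The largest simulated gap was below 10⁻¹⁵.

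**The case against.** The strongest reply is that the endpoint estimate is already adjusted. Table GZHA.1 defines these endpoints as changes from baseline, and the change models carry the covariate. The absolute-value analysis is additional, the protocol leaves the covariate optional, and every affected endpoint is exploratory in a study not powered for hypothesis testing. Escalation rests primarily on safety data (Protocol 7.4.1) and no interim statistical analysis is planned (SAP Section 10), so these models do not drive dosing. All of this stands. It limits the importance of the point but does not remove the unadjusted differences and CIs that the SAP says it will report.

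A reader might infer that baseline imbalance passes into the absolute-value contrast at full size. It does so only if the baseline-postdose slope is 1; otherwise it is scaled by the slope. For the same reason, the chance that at least one of six dose groups differs from placebo at baseline by more than 0.5 SD (about 87%) or 1 SD (about 22%) should not be read as the chance of an error that large in the estimate. The simulated chance of an expected shift above 0.5 SD in at least one dose group is about 0.5%, 22% and 58% at ρ = 0.3, 0.5 and 0.7.

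A reader might also take the precision loss as certain. It requires ρ above about 0.16. That is plausible for repeat measurements in one person, but nothing in the documents establishes it, least of all for fasting appetite ratings out to Day 29.

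**Conclusion.** The point holds for the additional absolute-value analyses of eight exploratory endpoints. They produce an unadjusted set of LY3493269-placebo differences that can depart from the adjusted set only through chance baseline imbalance, and the SAP does not say which set to interpret. A typical (one-SD) imbalance moves the contrast by 0.15 to 0.35 SD for ρ from 0.3 to 0.7, against a 90% CI half-width of 0.84 SD, with an SE 3.5% to 38% larger than needed.

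The figures assume pooled placebo, all six SC cohorts, equal SDs and the stated correlations. They do not apply if appetite moves to the non-parametric analysis that SAP 9.5.9 allows.

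The documents do not support reading this as bias or as a breach of the protocol. Random allocation keeps the unadjusted contrast unbiased on average, and Protocol 10.3.3.2 permits either choice. The practical weight is modest, but the correction is easy and worth making.

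**What to change.** In SAP 9.4.1 and 9.5.9, add baseline to the absolute-value models and restrict them to postdose values: `model value = baseline treatment timepoint treatment*timepoint`. Both scales then give the same drug-placebo difference, and the absolute-value table adds only least-squares means on the original scale.

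An equally valid alternative is one sentence naming the baseline-adjusted change model as the one for inference, with absolute values reported descriptively only.

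Either is a text and code edit using data already collected. The first option spends one degree of freedom and would cost at most about 1.3% in SE if baseline and postdose values were uncorrelated. The second costs no precision.
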